1.4 Potential Risks and Benefits

1.4.1 Potential Risks

Metformin- Risks

Metformin's most serious toxicity is lactic acidosis, occurring in three of 100,000 patient-years of use. Risk is significantly reduced when metformin use is avoided in those patients with hepatic, cardiac, or renal compromise. However, metformin's risk of lactic acidosis may be overstated since the recent evaluation of metformin associated lactic acidosis cases from 347 trials showed that the risk of lactic acidosis with metformin was not significantly increased compared with other antglycemic agents [88]. A common side effect of Metformin is diarrhea. Minor gastrointestinal upset is the most common toxicity, leading to cessation of therapy in less than 5% of individuals. Metformin does not induce hypoglycemia. While metformin alone is rarely associated with low blood sugars (hypoglycemia), it has been reported in cases where people are fasting or undergoing strenuous physical activity. It can also cause low blood sugars in patients with diabetes who are taking other medications to manage their blood sugars such as sulfonylureas

Doxycycline- Risks

Due to oral doxycycline's virtually complete absorption, side effects to the lower bowel, particularly diarrhea, have been infrequent. The following adverse reactions have been observed in patients receiving tetracyclines:

Gastrointestinal: Anorexia, nausea, vomiting, diarrhea, glossitis, dysphagia, enterocolitis, and inflammatory lesions (with monilial overgrowth) in the anogenital region. Hepatotoxicity has been reported rarely. These reactions have been caused by both the oral and parenteral administration of tetracyclines. Rare instances of esophagitis and esophageal ulcerations have been reported in patients receiving capsule and tablet forms of drugs in the tetracycline class.

Skin: Maculopapular and erythematous rashes. Exfoliative dermatitis has been reported but is uncommon.

Hypersensitivity reactions: Urticaria, angioneurotic edema, anaphylaxis, anaphylactoid purpura, serum sickness, pericarditis, and exacerbation of systemic lupus erythematosus.

Thyroid Gland Changes: When given over prolonged periods, tetracyclines have been reported to produce brown- black microscopic discoloration of thyroid glands. No abnormalities of thyroid function are known to occur.

Combination of these Agents:

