4.1.2 Exclusion Criteria

An individual who meets any of the following criteria will be excluded from participation in this study:

1. Subjects that do not have a baseline tumor specimen/biopsy prior to starting study medications.
 - a. Tumor specimens do not need to be at Jefferson at time of eligibility determination. Tumor specimens held at outside institutions should be requested for analysis of pre-treatment tumor vs post-treatment tumor.
2. Subjects who are pregnant or breastfeeding, or may become pregnant during metformin and doxycycline administration.
3. Received prior cancer therapy for the HNSCC that is being resected.
4. Subjects on metformin or doxycycline for any reason during the preceding 4 weeks.
5. Diabetic subjects that are managed by taking metformin or insulin
6. Subjects who have received iodinated contrast dye must wait 12 hours prior to starting Metformin. If a CT scan with contrast is scheduled after screening and consent, the metformin cannot be taken until after the CT with contrast has been completed and they have waited 12 hours.
7. Patients with serum creatine ≥ 1.5 mg/dL
8. Patients with history of lactic or any other metabolic acidosis.
9. Patients with history of congestive heart failure stage III or greater.
10. Patients scheduled for definitive cancer surgical resection less than 7 days from beginning of study drug administration or greater than 6 weeks from beginning study

drug administration.

11. Patients with history of hepatic dysfunction or hepatic disease and abnormal liver function tests defined as AST, ALT, Alk Phos, and or total bilirubin greater than 2.5 times the upper limit of normal. Patients who have a history of hepatic dysfunction or hepatic disease and normal liver function tests will be eligible to participate.
12. Patients with a current history (in the past 30 days) of heavy drinking which is defined in accordance with CDC definition as more than 8 drinks per week for women and more than 15 drinks per week for men. A standard drink contains .6 ounces of pure alcohol. Generally, this amount of pure alcohol is found in 12-ounces of beer, 8-ounces of malt liquor, 5-ounces of wine, 1.5-ounces or a "shot" of 80-proof distilled spirits or liquor (e.g., gin, rum, vodka, or whiskey). While on study, patients should limit their alcohol consumption to no more than 8 drinks per week for women and no more than 15 drinks per week for men.

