5.2 Study Product Description

Metformin:

Metformin is a biguanide drug currently approved for the treatment of type 2 diabetes mellitus by the FDA. It is currently being investigated in multiple cancer treatment trials.

Metformin is a therapeutic agent in the protocol. The initial starting dose will be 500mg orally daily for 3 days which then will be increased to 500 mg twice daily and, if tolerated, further increased to 1000mg twice daily after day 6. Patients will maintain 1000 mg twice a day dosing until the day prior to their scheduled definitive surgery. This dose schedule has been shown to be well tolerated and was able to promote cellular changes consistent with beneficial anti-cancer effects in breast cancer patients.

The treatments to be used in this trial are outlined in Table 1.

Doxycycline:

Doxycycline is an antibiotic provided in the formulation doxycycline hyclate. Doxycycline is virtually completely absorbed after oral administration. Following administration of a single 200 mg dose to adult volunteers, average peak serum doxycycline levels were 2.6 mcg/mL at 2 hours, decreasing to 1.45 mcg/mL at 24 hours. The mean Cmax and AUC 0-∞ of doxycycline are 24% and 13% lower, respectively, following single dose administration of DORYX tablets, 100 mg with a high fat meal (including milk) compared to fasted conditions. The mean Cmax of doxycycline is 19% lower and the AUC 0-∞ is unchanged following single dose administration of DORYX Tablets, 150 mg with a high fat meal (including milk) compared to fasted conditions. The clinical significance of these decreases is unknown.

Tetracyclines are concentrated in bile by the liver and excreted in the urine and feces at high concentrations and in a biologically active form. Excretion of doxycycline by the kidney is about 40%/72 hours in individuals with a creatinine clearance of about 75 mL/min. This percentage may fall as low as 1-5%/72 hours in individuals with a creatinine clearance below 10 mL/min.

Studies have shown no significant difference in the serum half-life of doxycycline (range 18-22 hours) in individuals with normal and severely impaired renal function. Hemodialysis does not alter the serum half-life.

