5.7 Concomitant Medications/Treatments

Medications or vaccinations specifically prohibited in the exclusion criteria are not allowed during the ongoing trial. If the patient is on any of the Class C medications as outlined in Section 5.4.2, they should be monitored closely for any potential interactions or side effects. If there is a clinical indication for one of these or other medications or vaccinations specifically prohibited during the trial, discontinuation from trial therapy or vaccination may be required. The investigator should discuss any questions regarding this with the Sponsor. The final decision on

any supportive therapy or vaccination rests with the investigator and/or the subject's primary physician. However, the decision to continue the subject on trial therapy or vaccination schedule requires the mutual agreement of the Investigator, the Sponsor, and the subject

All treatments that the investigator considers necessary for a subject's welfare may be administered at the discretion of the investigator in keeping with the community standards of medical care. All concomitant medication and therapies will be recorded on the case report form (CRF) including all prescription, over-the-counter (OTC), herbal supplements, and IV medications and fluids. If changes occur during the trial period, documentation of drug dosage, frequency, route, and date should also be included on the CRF. These will be cross referenced against the list of drugs in section 4.2 (Exclusion Criteria) to ensure that no agents that are contraindicated with metformin or doxycycline are used.

All concomitant medications received within 28 days before informed consent is signed and 30 days after the last dose of trial treatment should be recorded. Concomitant medications administered to treat SAEs and ECIs should be recorded as defined

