All medications are permitted except those that are contraindicated with metformin and doxycycline under current FDA recommendations. It is important to note that the medications that are contraindicated with metformin are contraindicated due to concern for theoretical interactions. Class C medications are allowed if they are established at baseline. The treating physician should be made aware of any new Class C medications taken during therapy for proper monitoring of potential interactions. The following is a list of medications identified as class C (monitor therapy) and class D (consider therapy modification) when treatment with metformin or doxycycline is considered:

Class C:

Carbonic anhydrase inhibitors
Cephalexin
Corticosteroids (orally inhaled)
Corticosteroids (systemic)
Dalfampridine
Dofetilide
Glycopyrrolate
Lamotrigine
Luteinizing hormone-releasing hormone analogs
Pegvisomant
Penicillin
Trospium

Class D:

Bismuth Subsalicylate
Cimetidine
Iodinated contrast agents
Somatropin

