C. Study treatment follow up phone calls will occur on days 3 and 5 ± 2 days of dose escalation to evaluate tolerability, document AEs, and concomitant medications. If patient remains on study drugs for >7 days, study treatment follow-up phone calls will occur a minimum of once a week until surgery to evaluate tolerability, AEs, and con meds. Last doses of metformin and/or doxycycline pills should not be taken within 12 hours of scheduled surgery.

D. Patient must receive a minimum of 7 days of metformin and/or doxycycline before having definitive surgery. Patients will stay on metformin and/or doxycycline until the day prior to surgery (up to the maximum of 5 weeks).

E. End of treatment visit may occur within 14 days ± 7 days of stopping study drug.

F. Correlative study blood to be collected the morning of surgical resection. Baseline samples are to be drawn after enrollment but prior to start of study treatment.

- G. Follow up phone call will be performed 30 days after last dose of study medication for any other side effects or toxicity and for pathologic staging information.
- H. serum or urine pregnancy test must be done within 14 days prior to enrollment on study for all women of childbearing potential
- I. If a confirmatory biopsy is performed at TJUH and excess tissue is available tissue will be flash frozen both at the time of biopsy and at the time of resection. A post-treatment tissue sample will be obtained from excess tissue taken from this resection specimen that is not needed in the course of clinical care.
- J. Study drug stopped the night prior to surgery.
- K. Concomitant medication reconciliation, and Toxicity and Adverse Event assessments should be done at every patient contact to fully capture any potential dose limiting toxicities or AEs that affect the patient's ability, willingness, and eligibility to continue taking study medications.
- L. Operative reports should be included with pathology reports in source documents when applicable.
- M. To be performed by a registered dietician, when possible. Must meet with patient within five days of enrollment and record the patient's last 3 days of caloric intake and estimate their caloric intake versus their caloric needs per the Harris Benedict Equation. It will be noted in the patient chart if these assessments could not be completed.
- N. Pre-operative nursing or anesthesia exam is acceptable and is to be performed the morning of surgery.

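### Diabetics on glucose-lowering drugs other than metformin or insulin can enter the metformin arms, yet the close-monitoring rule misses them although Section 1.4.1 names their risk of low blood sugar

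*Combined protocol and SAP*

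**What the plan says.** **Risk.** Section 1.4.1 is mixed. It opens reassuringly: "Metformin does not induce hypoglycemia. While metformin alone is rarely associated with low blood sugars (hypoglycemia". It mentions reports during fasting or hard exercise, and then adds: "It can also cause low blood sugars in patients with diabetes who are taking other medications to manage their blood sugars such as sulfonylureas".

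**Eligibility.** Section 4.1.2, item 5, excludes "Diabetic subjects that are managed by taking metformin or insulin". Item 4 excludes anyone who has taken either study drug in the previous four weeks. Item 14 excludes patients on drugs that FDA recommendations treat as contraindicated with metformin or doxycycline, and lists four Class D entries.

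**Other drugs during the trial.** The default in Section 5.7 is: "All medications are permitted except those that are contraindicated with metformin and doxycycline under current FDA recommendations". A stricter rule applies to one group: "If the patient is on any of the Class C medications as outlined in Section 5.4.2, they should be monitored closely". The Class C and D lists are printed later in the same section.

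**Dose and contacts.** Under Section 5.2 metformin starts low and is, "if tolerated, further increased to 1000mg twice daily after day 6". Section 6, schedule note C, plans phone calls "to evaluate tolerability, document AEs, and concomitant medications", at least weekly once treatment passes day 7. Note K adds: "Concomitant medication reconciliation, and Toxicity and Adverse Event assessments should be done at every patient contact".

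**The concern.** The protocol identifies a group in which metformin can lower blood sugar. It also has a rule for watching some patients more closely because of their other drugs. The two are not connected. If the eligibility and monitoring rules are followed exactly, a diabetic on a sulfonylurea can be randomised to arm A or C and reach 2000 mg of metformin daily without coming under the closer rule.

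What is at stake is patient safety for a few people. With no glucose in the laboratory schedule, low blood sugar would be noticed through symptoms, so it matters whether the patient recognises them and whether the caller asks. Fasting is one of the circumstances mentioned in Section 1.4.1, and Sections 1.2 and 1.3 allow that some patients may already be eating below their needs. That is not the same as fasting, but it makes the question worth asking.

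**Working it through.** The plan gives no figure to reproduce. The check sets the rules side by side and then counts what the documents allow to be counted.

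1. **Group named at risk (1.4.1).** Diabetics on other glucose-lowering drugs, for example sulfonylureas.

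2. **Exclusions (4.1.2) applied to a diabetic on a sulfonylurea alone.**
   - Item 4 (either study drug in the last four weeks): not met.
   - Item 5 (managed with metformin or insulin): not met.
   - Item 14 (contraindicated drugs): met only if sulfonylureas are contraindicated with metformin, which the documents do not say. The Class D entries are bismuth subsalicylate, cimetidine, iodinated contrast agents and somatropin.
   - Result: eligible. A patient who also takes metformin or insulin is not.

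3. **Close-monitoring rule (5.7).** Class C entries 12 + Class D entries 4 = 16, of which 0 are diabetes drugs. The patient falls under the general permission, not the closer rule.

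4. **Safeguards that do reach this patient.**
   - Physician review of baseline results and full information before enrolment (Section 4), and discussion of risks at consent (14.3).
   - Medical history with attention to diabetes (7.1), with no action attached.
   - Escalation only if tolerated (5.2); tolerability calls, an instruction to report toxicity, and CTCAE-based dose rules (5.4, note C).
   - Adverse event and medication review at every contact (note K).
   - Laboratory tests: creatinine, liver tests and blood count, scheduled at screening only (Section 6 with note B, 7.2.1). Glucose is not listed.
   - Result: all are general. The dose rules act only after an event has been recognised.

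5. **Exposure and opportunity.**
   - Metformin arms: 11 + 11 = 22 of 33 patients. Arm B receives doxycycline alone and is not concerned.
   - Days at 2000 mg daily, if tolerated, with that level starting on day 7 (Table 1): a 7-day course gives 7 − 7 + 1 = 1 day; a 35-day course gives 35 − 7 + 1 = 29 days.
   - Scheduled calls: 2 around the two dose steps, then weekly. A 7-day course gives 2; a 35-day course gives 2 + (35 − 7)/7 = 6.

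No prevalence of sulfonylurea use and no rate of low blood sugar is given, and none is assumed here.

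**The case against.** The strongest reply is that the general machinery already does the work. Symptomatic low blood sugar is an adverse event under Section 8.1.2, and adverse events are sought at every contact. All concomitant drugs are recorded, diabetes is noted in the history, and the investigator may withdraw a patient for safety (4.4.1). Sections 4 and 14.3 require that patients be informed of the risks, and Section 1.4.1 lists this one. Naming one symptom to ask about is a level of detail that the Manual of Procedures mentioned in Section 15.5 may contain. The close-monitoring phrase is itself undefined, so attaching these patients to it adds little.

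Much of this stands. A reader might infer that these patients receive no written warning about low blood sugar. The documents do not support that: a general duty to inform exists, and the consent pages are not in the copy reviewed. Nor are these patients unmonitored. It also stands that the benefit comes from the symptom briefing and question, not from the monitoring label.

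The reply does not remove the mismatch. The protocol chose to single out some concomitant drugs for closer attention, and its list omits the drug class that its own risk section names. General adverse event questions depend on the patient linking symptoms to blood sugar, and no scheduled laboratory test would reveal the problem otherwise.

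**Conclusion.** The concern holds in a narrow form and is a matter to consider, with medium confidence. Diabetics who take a glucose-lowering drug other than metformin or insulin are eligible for arms A and C, are named in Section 1.4.1 as a group in which metformin can lower blood sugar, and fall outside the closer-monitoring rule. The safeguards that reach them are general.

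Two stronger readings should be avoided. The first is that every diabetic not on insulin is eligible: exclusions 4 and 5 also remove metformin users. The second is that 22 of 33 patients are at risk: that is the number planned to receive metformin. The number affected is unknown, likely small and possibly zero, and the protocol describes low blood sugar on metformin alone as rare.

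The conclusion assumes that the eligibility and concomitant-drug rules are applied as written, that item 14 does not reach sulfonylureas, and that counselling is not already set out in the consent form or Manual of Procedures. If it is, the briefing part of the fix is already met. The primary endpoint, the power calculation and the analysis are unaffected.

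**What to change.** Leave the Class C list as it is and add to Section 5.7:

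> *Exclusions 4, 5 and 14 are unchanged. Otherwise eligible patients with diabetes who take a sulfonylurea or another glucose-lowering drug (other than metformin or insulin) are also monitored closely. In arms A and C they are told the symptoms of low blood sugar before the first dose and asked about them at each scheduled tolerability call.*

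Add a matching line to schedule note C. The opening sentence keeps the addition from being read as admitting metformin or insulin users. The same edit could correct the pointer to Section 5.4.2, which does not appear in the text; the Class C list is in Section 5.7.

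Alternative, at the investigator's choice: extend exclusion 5 to metformin, insulin or a sulfonylurea.

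Cost: three sentences and one line, with no new visit or laboratory test. In practice it means a short briefing before the first dose and one extra question on about 2 to 6 existing calls for a few patients. Under the alternative, the cost is the loss of a few candidates.

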- To assess the effect metformin, doxycycline, or metformin and doxycycline therapy on the metabolic state of the patient as characterized serologically by: adipokines and the IGF-1/insulin signaling pathways through assessment of serum triglycerides, IGF-1, IGF-BP3, erythrocyte sedimentation rate, adiponectin, leptin, IGF-1R, exosome evaluation, metabolomics profile, and microRNA expression profiles and physiologically by performing a nutritional assessment via a nutritionist-mediated 3 day dietary recall and comparing a patient's estimated dietary intake against their estimated caloric needs.

Population: Patients aged 18 years and above.

Known or suspected head and neck squamous cell carcinoma

Have a surgical resection planned as a part of their therapy

Normal organ function including creatinine less than or equal to 1.5mg/dL

Phase: II

Number of Sites: Thomas Jefferson University Hospital

Description of Intervention: Metformin and doxycycline are the therapeutic agents. The initial starting dose of metformin will be 500 mg orally daily for 2 days which will then be increased to 500 mg orally twice daily, and if tolerated, further increased to 1000 mg twice daily after day 6. Subjects will maintain the maximum tolerated dose (up to 1000 mg twice daily) until the day prior to their scheduled definitive surgery.

For doxycycline the patients will take 100 mg by mouth every twelve hours until the day prior to their scheduled definitive surgery.

[figure not shown]
Study Duration: 40 months

Subject Participation Duration: From the time that patients receive their biopsy and enroll in the trial until their definitive surgery is between 1-5 weeks. The patients will be called 30 days after surgical resection to determine if there were any further adverse effects of the medications given.

Estimated Time to Complete

Enrollment:

Schematic of Study Design:

1 Introduction

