3.2 Number of Subjects

33 total, 11 in each arm

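### Exclusion item 11, as worded, admits a patient with liver tests above 2.5 × ULN and no liver history

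*Combined protocol and SAP*

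**What the plan says.** Section 4.1.2, item 11, excludes "Patients with history of hepatic dysfunction or hepatic disease and abnormal liver function tests defined as" any of AST, ALT, alkaline phosphatase or total bilirubin above 2.5 × ULN. It then adds: "Patients who have a history of hepatic dysfunction or hepatic disease and normal liver function tests will be eligible to participate".

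Other places bear on the same question:

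- Study Summary, Population, asks for "Normal organ function including creatinine less than or equal to 1.5mg/dL".
- Section 1.4.1, on metformin and lactic acidosis: "Risk is significantly reduced when metformin use is avoided in those patients with hepatic, cardiac, or renal compromise". On tetracyclines it says: "Hepatotoxicity has been reported rarely".
- Section 4.1.2, item 7 (renal): "Patients with serum creatine ≥ 1.5 mg/dL". Item 9 (cardiac): "Patients with history of congestive heart failure stage III or greater".
- Section 5.4, in defending the contrast rule, counts liver dysfunction among the conditions this trial excludes and attaches no requirement of a prior history.
- Calendar note B in Section 6 and the laboratory list in Section 6.1 print the 2.5 × ULN figure after the liver tests, but state no rule. The lists in Sections 4.3, 7.1 and 7.2.1 carry no threshold.

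**The concern.** Current liver test results are the direct evidence of hepatic compromise at the time of dosing. Under item 11 they count only if the patient also has a liver history, so markedly raised tests that come to light only at screening do not exclude.

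This matters because eligibility is settled before randomization, and two of the three arms contain metformin. The doxycycline arm is not wholly outside the question, given the rare hepatotoxicity noted for the class. Screening is also the only scheduled chemistry: the Section 6 calendar shows it once, and Sections 6.3 and 6.4 list no liver tests at surgery or end of treatment. The entry criterion is therefore the only written rule that acts on a scheduled liver test.

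**Working it through.** The plan gives no figure to reproduce here. The check is a reading of the criteria, followed by simple counts.

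**Step 1. How the two conditions combine.** Three readings of item 11 are possible.

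- Both a liver history and a test above 2.5 × ULN are needed. This agrees with the second sentence.
- A history excludes, and separately abnormal tests exclude. The second sentence contradicts this, because it admits a history with normal tests.
- Hepatic dysfunction excludes outright, and hepatic disease excludes only with abnormal tests. The second sentence contradicts this too, because it admits a history of either with normal tests.

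Only the first reading survives.

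**Step 2. The four combinations.** Item 11 defines abnormal as above 2.5 × ULN, so normal is taken here as at or below it.

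| Liver history | Any test > 2.5 × ULN | Item 11 as worded | Rule on the tests alone |
|---|---|---|---|
| Yes | Yes | Excluded | Excluded |
| Yes | No | Eligible | Eligible |
| No | Yes | **Not excluded** | **Excluded** |
| No | No | Not excluded | Not excluded |

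Item 11 excludes 1 of 4 combinations and a rule on the tests alone excludes 2 of 4. Only the third row changes.

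**Step 3. Whether another criterion catches the third row.** Inclusion items 1 to 7 include a creatinine limit but nothing on the liver. Exclusion items 1 to 10 and 12 to 14 set no liver-test limit. Item 12 concerns recent heavy drinking, not test results. Nothing catches it.

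**Step 4. Comparison with the other two conditions named in Section 1.4.1.** Renal compromise is excluded on the creatinine value alone (item 7). Cardiac compromise is excluded on history of a given severity, with no test required (item 9). Hepatic compromise is the only one that needs both a history and a current laboratory finding, and no section says why.

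**Step 5. Exposure.** Section 3.2 gives "33 total, 11 in each arm", and Section 3 puts metformin in arms A and C: 2 × 11 = 22, and 22 / 33 = 66.7%. This is the share of all planned patients who receive metformin, not the number affected by the gap.

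**Step 6. Scale of the lactic acidosis risk.** Section 1.4.1 gives three cases per 100,000 patient-years, and Section 1.2 caps metformin at 35 days.

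- Maximum exposure: 22 × 35 = 770 patient-days; 770 / 365 = 2.11 patient-years.
- Expected cases at the general rate: 2.11 × 3 / 100,000 = about 0.00006.

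That rate is for general use. The documents give none for patients with raised liver tests.

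**The case against.** The strongest reply is that the intent is plain and a site reading the whole protocol would probably not enroll this patient. The Summary, Section 5.4 and the threshold printed in the two laboratory lists all point to exclusion, and Section 4 has the principal investigator or treating physician review baseline results before entry. This lowers the practical risk. It does not supply the rule: that review verifies the listed criteria, which this patient passes. Section 5.4 is a passing remark without a threshold. Withdrawal for a laboratory abnormality under Section 4.4.1 is discretionary and comes after entry.

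Other points limit how strongly the concern can be put:

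- Section 1.4.1 does not define hepatic compromise. It does not say that, for example, a raised alkaline phosphatase alone would qualify. The 2.5 × ULN boundary comes from item 11, so the threshold needs clinical confirmation.
- The absolute risk is small at the general-use rate, and Section 1.4.1 itself says the lactic acidosis risk may be overstated.
- Item 9 has a severity cut-off, so milder heart failure is admitted, and the cardiac comparison is looser than the renal one.
- The hepatotoxicity remark describes a drug effect and is not tied to raised baseline tests.
- Counting combinations says nothing about how many patients fall in each.
- The second sentence says normal, so a history with tests between 1 and 2.5 × ULN is not expressly admitted. Step 2 treats it as eligible on item 11's own definition.

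All of these stand as limits on emphasis. None changes the third row of the table.

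**Conclusion.** The concern holds. Followed as written, item 11 does not exclude a patient whose liver tests exceed 2.5 × ULN and who has no liver history, and no other criterion does. This is a stated safety rule that gives a result the protocol's own rationale argues against, rather than a missing detail, and it should be corrected.

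The gap is one combination of the four. The number of patients it would affect cannot be estimated from the documents. The conclusion rests on the literal wording of item 11 and on taking its 2.5 × ULN figure as the intended boundary. It is not a claim that harm is likely, and the sample size and the primary signed-rank analysis are unaffected.

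**What to change.** Reword item 11 along these lines: *Patients with AST, ALT, alkaline phosphatase or total bilirubin above 2.5 × ULN at screening, whether or not they have a liver history. A liver history with all four values at or below 2.5 × ULN does not exclude.* This also settles the case of a history with mildly raised tests.

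Remove the stray threshold from calendar note B and from Section 6.1, and refer to item 11 there instead. The investigators should confirm that 2.5 × ULN is the limit they want.

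The cost is one reworded criterion and two laboratory-list lines in an amendment. All four tests are already on the screening lists in note B and Section 6.1, so no new blood test is needed. The downside is possibly a few more screen failures.
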